1.3 Improve the awareness rate of kidney disease in CVD patients

However, awareness of CKD has remained low¹⁹. An international cohort of 3 million patients with diabetes or hypertension found that the overall UACR detection rate for diabetes and hypertension was only 35.1% and 4.1%²⁰. A recent Swedish study found that among more than 50,000 patients who met diagnostic criteria for CKD (i.e., at least two eGFR < 60 mL/min/1.73m² separated by more than 3 months), only 23% of patients had a diagnosis of CKD in their electronic health records²¹. The NHANES study found that the awareness rate of CKD is much lower than that of hypertension and diabetes²². In a NHANES study, the awareness rate of CKD patients with severe renal function decline was 41.8%, while the awareness rate of CKD patients with mild to moderate renal function decline was only 7.8%²³. In the KEEP study, the awareness rates of patients with the above two conditions were 32.1% and 5.4%, respectively²⁴. More importantly, patients with eGFR>60 mL/min/1.73 m² and elevated urinary protein account for more than 40% of CKD patients, but urinary protein detection rates were low, and physicians and patients are more aware of this type of CKD²⁵. This missed diagnosis may have adverse consequences for

patient care, as the use of nephrotoxic drugs is more common in undiagnosed CKD patients²⁶. Therefore, in the Healthy People 2030 plan in the United States, improving the awareness rate of CKD continues to be listed as a priority national public health goal by the health department²⁷.

In China, the prevalence of albuminuria measurement in CVD patients is still unclear, and there is limited data on the prevalence of albuminuria in patients with T2DM in the Department of Cardiology. Further research is needed to increase relevant data to better guide the diagnosis and treatment of CVD patients.

2. Research objectives

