4.1 Study data collection plan

The PLACARD study will be a cross-sectional observational study that collect patient information only once after screening and retrace the case system after the first visit, without any follow-up. It is expected that each center will complete the screening and

enrollment of patients within one month.

During the information collection period the investigator will:

1. Sign the informed consent form: Before signing the informed consent form, the participants should be fully informed of the research purpose and how the data will be used, and the researcher should also sign the informed consent form. The investigator and the patient each keep an original signed informed consent form;

2. Patient screening form: After signing the informed consent form, it will be confirmed whether the patient meets all the inclusion criteria and not all exclusion criteria, and the screening information will be recorded in the patient screening form. In order to ensure the continuity of screening, the screening information of potential patients who failed to enroll will also be recorded in the patient screening form;

3. After the patients are enrolled, the researchers should complete the following tasks and collect relevant data:

- Demographic information: gender, date of birth, education, type of medical insurance;
- Patient history: T2DM, hypertension, hyperlipidemia, coronary heart disease, atrial fibrillation, heart failure, stroke (ischemic and hemorrhagic), transient ischemic attack (TIA), cataracts, and macular degeneration;
- History of surgical intervention: coronary intervention, coronary artery bypass grafting and coronary angiographic stenosis;
- Questionnaire: Edinburgh Intermittent Claudication Questionnaire (ECQ) ;
- Physical examination: blood pressure, heart rate, height and weight;
- Clinical assessment information: blood glucose (including HbA1c , fasting blood glucose,

two-hour postprandial blood glucose), renal function (including serum creatinine glomerular filtration rate, UACR), blood lipids (including total cholesterol, LDL cholesterol, HDL Cholesterol, triglycerides), funduscopy, and the detection frequency of the above inspections in the past year (mainly based on patient self-report);

- Whether the doctor prescribes urine routine examination for inpatients, and whether the doctor issues a new doctor's order after the outpatients report back the renal function examination;

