- Combined drug information: this prescription drug and commonly used drugs (outpatients) and medications during hospitalization (inpatients);
- Information about patient behavior: smoking history and drinking history;
- UACR value detected on the day of enrollment;
- The result of funduscopy gained on the day of enrollment.

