4.3 Research procedure

The patient recruitment consisted of two parts, 50 patients from outpatients attending the Department of Cardiology and 50 from in patients receiving treatment in the Department of Cardiology.

- In the outpatient department, a selected, representative cardiologist should be followed and eligible patients among the physician's visits would be continuously screened. It is necessary to communicate with the person in charge of the Department of Cardiology

[figure not shown]
before the start of the branch center to determine the following outpatient doctors, and plan and determine the enrollment process with the outpatient doctors in advance. On the screening day, record and follow the T2DM patients encountered by the doctor during the consultation process, communicate with the patient for informed consent, screen according to the inclusion criteria, and generate a study number for those who meet the enrollment criteria (see flow chart 1).

- In the ward selected by the inpatient department of the Department of Cardiology, the clinical coordinator conducts a preliminary examination of all inpatients in the ward through the hospital medical record system, records the patient with T2DM, and communicates with the patient for informed consent, according to the inclusion and exclusion criteria, screening is carried out, and those who meet the inclusion conditions are enrolled and a research number is generated (see flow chart 2).

[figure not shown]
A face-to-face questionnaire should be conducted on the enrolled patients and baseline information such as, medical history, clinical assessment information, medication information, and living habits should be collected; and physical examination, UACR tests and funduscopy were performed on the patients. For outpatients, it is also necessary to query all the medical records of the enrolled patients on the day after the day of enrollment to supplement any missing information.

To evaluate the doctor's attention to chronic kidney disease, this study mainly reviewed the doctor's order to observe whether the doctor prescribes the UACR checklist for patients with T2DM to monitor the renal function of the patients. If the doctor has issued a UACR test for the patient, record the inspection value; if the doctor has not prescribed the test, use the

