UACR measurement equipment provided in this study to obtain the results. When all the research-related information of the enrolled patients is collected, and the UACR results are obtained and fed back to the doctors, the data collection process is deemed to be over. In addition, after the doctor obtains the results of the UACR examination, whether to revise the doctor's order based on the detected nephropathy is also one of the ways to measure the doctor's awareness of the identification and management of the nephropathy of diabetic patients in the cardiology department.

Flowchart 1, Outpatient enrollment process

Flowchart 2, Inpatient enrollment process

5 Research evaluation

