5.3 Laboratory inspection

During the study period, dry urine cups will be taken and fresh randomized mid stage urine samples will be collected from patients in the study group. Portable urine testing instruments (such as the Mission ACON U120 Ultra/EMPSUN Enpusen urine testing machine and 14 test strips, which are purchased by the sponsor and provided to each center, are used to measure the patient's microalbumin and urine creatinine data by using dry chemical methods, namely test strips, see appendix 2). And the UACR value will be calculated by using the formula $UACR(mg/g) = \text{urine microalbumin}(mg/L) * 1000 / (\text{urine creatinine}(mmol/L) * 0.113)$.

During the study period, portable fundus cameras (which are purchased by the sponsor and provided to each center, with equipment examples shown in appendix 3) will be used to take fundus photos of enrolled patients, and the results obtained immediately will be fed back to the doctors and patients.

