5.4 Physician behavior and kidney disease management

After collecting the urine sample and calculating the UACR value, the patient will feed back the test results to his/her doctor. This study will record the doctor's current diagnosis, and use the method of reviewing medical records to evaluate whether he/she provides a new diagnosis and prescription for the patient's renal function.

6 Statistical Considerations

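### Section 4.3 lets the doctor's ordering decide how UACR is measured for the primary endpoint, while 5.3 and 5.4 describe the strip test without that exception

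*Protocol*

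**What the plan says.** Protocol section 4.3 gives an order of precedence: "If the doctor has issued a UACR test for the patient, record the inspection value; if the doctor has not prescribed the test", staff turn to the "UACR measurement equipment provided in this study to obtain the results". The same paragraph says that the doctor's ordering of UACR is reviewed as a sign of attention to kidney disease.

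Section 5.3 describes the laboratory step without reference to an ordered test: "fresh randomized mid stage urine samples will be collected from patients in the study group", the supplied strips measure albumin and creatinine, "And the UACR value will be calculated by using the formula" given there. Section 5.4 starts from the same point: "After collecting the urine sample and calculating the UACR value", the result goes back to the doctor.

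The data list in 4.1 asks for the "UACR value detected on the day of enrollment". It also lists UACR under renal function among the clinical assessment items, and 5.2 retrieves recent test results, including renal function, from the last three months of records. The ordering item in 4.1 is "Whether the doctor prescribes urine routine examination for inpatients"; for outpatients it is a new order after the result is reported back.

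The primary endpoint in 6.3.1 is the prevalence of UACR at or above 30 mg/g.

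**The concern.** The primary endpoint is a proportion above a cut-off, so it depends on how each value is measured. Under 4.3 a patient whose doctor ordered a UACR contributes that result, and every other patient contributes a strip result. The source is thus set by a behaviour that the study itself wants to describe. If the two sources classify differently at 30 mg/g, the pooled prevalence is a mixture whose weights are the ordering rate. It would also change if a centre read 5.3 as applying to everyone.

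This cannot be left to the analysis stage. There is no follow-up (3.5) and samples are destroyed after analysis (7.1.2), so a strip value not taken on the day is lost.

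**Working it through.** **1. Reading the sections together.** Sections 4.1, 4.3 and 5.3 can be joined as follows: one enrolment-day value, from the ordered test if there is one and otherwise from the strip. That settles the date through 4.1. It does not settle the method, because 4.3 names no assay for the ordered value and gives no date of its own. The renal-function item in 4.1 and the record search in 5.2 may already capture a record-based UACR. The order review in 4.3 and the instrument reports in 7.1.3 may allow the source to be reconstructed. No section says that the strip is run in every patient or that the source is recorded.

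**2. The plan's own precision.** Section 6.6 assumes p = 0.50 and n = 3,000. Half-width = 1.96 × √(0.25/3000) = 1.79 points, so the interval is 48.2% to 51.8%, width 3.6. The stated figure reproduces.

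**3. Illustration of what the choice of rule could move.** Inputs:
- p = 0.50, from 6.6.
- r, the share with an ordered test. The protocol gives no rate for its own centres. Section 1.3 cites an external cohort in which the "UACR detection rate for diabetes and hypertension was only 35.1% and 4.1" per cent. I borrow 0.351 as the working value and 0.041 only as a low value.
- Strip sensitivity and specificity (Se, Sp): assumed, as the protocol gives none.
- The ordered value is taken as the reference, and true prevalence as the same with and without an order: both assumed.

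Shift caused by the strip: s = p·Se + (1−p)(1−Sp) − p.
- 0.80/0.95: 0.400 + 0.025 − 0.500 = −7.5 points
- 0.90/0.90: 0.450 + 0.050 − 0.500 = 0
- 0.95/0.85: 0.475 + 0.075 − 0.500 = +5.0 points

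Expected prevalence is p + s with strips for all, and p + (1−r)s under 4.3. The difference between the rules is r·s:
- r = 0.351: −2.63 to +1.76 points
- r = 0.041: −0.31 to +0.21 points

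Bias against the assumed reference is s = −7.5 to +5.0 points with strips for all. Under 4.3 with r = 0.351 it is 0.649·s = −4.9 to +3.2 points.

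**4. The formula in 5.3 (a separate error).** It divides albumin (mg/L) × 1000 by creatinine (mmol/L) × 0.113. Since mmol/L × 0.113 is already g/L, mg/L divided by it is already mg/g. Albumin 10 mg/L with creatinine 10 mmol/L gives 10/(10 × 0.113) = 8.85 mg/g. The printed formula gives 10 × 1000/(10 × 0.113) = about 8,850. The protocol's own Figure 1 confirms this: it pairs 3 mg/mmol with 30 mg/g, and 3/0.113 = 26.5, whereas the printed formula gives about 26,549. With the factor in place, a true ratio of 30/1000 = 0.03 mg/g would already reach the cut-off.

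**The case against.** The strongest reply is that nothing conflicts: 4.3 says when the device is used and 5.3 says how it is run. Section 5.3 speaks of patients in the study group, not of every patient, so a reader who infers a flat contradiction goes further than the text. The two enrolment flowcharts could not be read in the copy consulted and may clarify the step. This reply stands as far as it goes. But if 4.3 governs, the dependence on ordering follows directly.

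Three stronger readings are also tempting, and the protocol does not support them:
- *That the prevalence estimate is biased by a known amount.* Strip accuracy, the assay behind an ordered test and the ordering rate are all absent, and some plausible inputs give zero. The 1.8-point half-width also ignores clustering. With an assumed intraclass correlation of 0.02 and 100 patients per centre it would be 1.79 × √(1 + 99 × 0.02) = 3.1 points, so even −2.6 lies inside it. The comparison gives scale only; a systematic shift is not sampling error and does not shrink with sample size.
- *That contrasts between patient groups are distorted.* This needs ordering rates that differ between groups. The diabetes and hypertension rates in 1.3 cannot supply such a gap, because every participant here has type 2 diabetes.
- *That the strip must be the only primary source.* On the assumptions above, strips for all would enlarge the pooled bias while making patients comparable. Which value should define the endpoint is a judgement for the sponsor.

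**Conclusion.** The point holds in a limited form. Section 4.3, followed as written, lets the doctor's ordering choose the measurement source for the primary endpoint. Sections 5.3 and 5.4 do not state that exception, and no section guarantees either a strip value in everyone or a record of source. It deserves correction because the missing value cannot be recovered later, not because a bias has been shown. The range of -2.6 to +1.8 points rests wholly on assumed strip accuracy, a borrowed ordering rate, an ordered test treated as error-free and equal true prevalence by ordering. It includes zero, and at a 4.1% ordering rate it is negligible.

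The formula error is independent of the source question and needs no such assumptions: as printed, the result is 1,000 times too large.

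**What to change.** - Reconcile 4.3 with 4.1, 5.3 and 5.4.
- Take the enrolment-day strip value in every enrolled patient.
- Record any doctor-ordered UACR separately, with its source and date.
- State in advance which of the two values defines the primary endpoint. Report prevalence by source, with the alternative definition as a sensitivity analysis.
- If data were already collected under 4.3, report prevalence by source and state that source is entangled with the reason for testing.
- Separately, remove the factor 1000 from the 5.3 formula as long as creatinine is entered in mmol/L.

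The cost is one extra strip per patient with an ordered test (3,000 × 0.351 = 1,053 strips at the borrowed rate), plus two data fields. Devices and strips are already supplied to every centre. The downside is that a uniform strip gives comparability but keeps the strip's own error, which is why the ordered value should be kept and the second definition reported.

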5.1 Clinical evaluation

During the study period, the clinical data and demographic data of the enrolled patients will be measured and recorded, including gender, age, height, weight, as well as disease history, drug history, smoking status, and drinking status. The physical examination will also collect basic physiological data such as blood pressure and heart rate to assess the patient's basic physical characteristics.

5.2 Medical record inquiry

The indicators examined will be retraced by querying the HIS electronic medical record system. The medical records will be queried for the most recent transcripts of relevant tests such as blood glucose, lipids, blood tests and renal function of the enrolled patients in the last three months, to check for logical matches of disease or medication history, and combined with the patient's self-reported record of the frequency with which he/she has

monitored and managed the indicators in the past year.

5.3 Laboratory inspection

During the study period, dry urine cups will be taken and fresh randomized mid stage urine samples will be collected from patients in the study group. Portable urine testing instruments (such as the Mission ACON U120 Ultra/EMPSUN Enpusen urine testing machine and 14 test strips, which are purchased by the sponsor and provided to each center, are used to measure the patient's microalbumin and urine creatinine data by using dry chemical methods, namely test strips, see appendix 2). And the UACR value will be calculated by using the formula $UACR(mg/g) = \text{urine microalbumin}(mg/L) * 1000 / (\text{urine creatinine}(mmol/L) * 0.113)$.

During the study period, portable fundus cameras (which are purchased by the sponsor and provided to each center, with equipment examples shown in appendix 3) will be used to take fundus photos of enrolled patients, and the results obtained immediately will be fed back to the doctors and patients.

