1.2 Evaluation of renal function

Based on eGFR and proteinuria levels, the KDIGO guidelines divide CKD into 5 eGFR levels and 3 proteinuria stages (Figure 1) to judge the prognosis of patients. eGFR is one of the reliable indicators to reflect renal function, but its clinical use has certain limitations. Firstly, eGFR is calculated based on serum creatinine levels, which are affected by a variety of

factors, including muscle mass, extrarenal excretion, and dietary factors. Secondly, the eGFR formula is established based on population data and is not applicable to all kidney diseases. Furthermore, the presence of CKD as judged by eGFR alone means that 50% of kidney function has been lost¹⁶.

CKD Category				Classification of Albuminuria		
				A1	A2	A3
				Normal and slightly elevated	Moderately elevated	Severely elevated
				<30 mg/g <3 mg/mmol	30-299mg/g 3-29 mg/mol	≥300mg/g ≥30mg/mmol
Classification of eGFR (ml/min/1.73m ²)	G1	Normal renal function	≥90			
	G2	Mild decline	60-90			
	G3a	Mild to moderate decline	45-59			
	G3b	Moderate to severe decline	30-44			
	G4	Severe decline	15-29			
	G5	Renal failure	15			

Figure 1. Classification and prognosis of chronic kidney disease (CKD) according to the 2012 KDIGO guidelines

UACR is a guideline recommended indicator for monitoring the risk of early kidney injury in T2DM and kidney related diseases, which can reflect early kidney disease and kidney injury. UACR measures the ratio of albumin to creatinine in a single urine sample and is a reliable method for monitoring urinary protein excretion¹⁷. UACR between 30 and 300mg/g is defined as microalbuminuria, and UACR >300mg/g is defined massive proteinuria. UACR can reliably reflect the 24-hour urinary protein volume, and is fast, simple, and accurate. It

is an ideal clinical indicator for qualitative and quantitative diagnosis of albuminuria¹⁸. Thus, given the high cost of CKD treatment and the low cost of detecting albuminuria, as well as the need to identify previously unrecognized patients at high CVD risk, the 2021 ESC Cardiovascular Prevention guidelines recommend that systematic evaluation of urinary protein be considered in all men older than 40 and all women older than 50 (or postmenopausal)¹⁴.

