6.3 Outcome Analysis

6.3.1 Main endpoint

The primary endpoint of this study will be the prevalence of albuminuria (UACR \geq 30 mg/g) in patients with type 2 diabetes presented to the Department of Cardiology , and the prevalence of albuminuria and other demographic characteristics will be assessed by descriptive abstracts. In summary, the relationship between the stage of renal impairment/disease (A1-A3 or GFR classification) and relevant covariates was analyzed by logistic regression model. Crude ORs and multivariate-adjusted ORs will be reported, including covariates including:

Age group (18-39 years old, 40-59 years old, 60-69 years old, \geq 70 years old); gender; BMI group (18.5, 23.9, 27.9, 28), blood pressure, blood lipid (LDL, HDL, TG), living habits (smoking, drinking); sub-research centers, nephrotoxic drugs being used, disease history.

Prevalence will be analyzed grouped by stratification factors, gender and age, geographic

region (East, South, Central, North, Northwest and Southwest), etc.

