6.4.2 Secondary endpoints

(1) Albuminuria level in patients with T2DM in the Department of Cardiology (microalbuminuria means UACR value >30 and <300 mg/g; macroalbuminuria means UACR value ≥ 300 mg/g);

(2) The prevalence and level of albuminuria in different types of cardiovascular diseases in the Department of Cardiovascular Medicine (microalbuminuria refers to UACR values >30 and <300 mg/g ; macroalbuminuria refers to UACR values ≥ 300 mg/g);

(3) Different treatment patterns for patients with CKD and patients without CKD;

(4) Assessing the current status of disease-related risk factor management in patients with T2DM attending cardiovascular medicine departments at different levels of hospitals;

(5) Evaluating the management of complications in patients with T2DM in different levels of hospitals.

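### The UACR formula in Protocol section 5.3 carries a surplus factor of 1,000; applied as written, it would class nearly every strip-tested patient as macroalbuminuric

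*Protocol*

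**What the plan says.** Section 5.3 (Laboratory inspection) has a portable strip reader measure urine albumin and creatinine, and fixes how the ratio is formed: "And the UACR value will be calculated by using the formula $UACR(mg/g") = albumin in "mg/L) * 1000 / (\text{urine creatinine}(mmol/L) * 0.113"). The inputs are thus albumin in mg/L and creatinine in mmol/L, and the output is labelled mg/g.

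Section 1.2, Figure 1, gives the albuminuria classes in both units. The A1 class is "<30 mg/g <3 mg/mmol", and A3 starts at 300 mg/g, paired with 30 mg/mmol.

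Section 6.3.1 defines the primary endpoint as the "prevalence of albuminuria (UACR \geq 30 mg/g") in the study population. Section 6.4.2 adds the upper class: "macroalbuminuria means UACR value ≥ 300 mg/g".

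Section 4.3 settles which patients the formula reaches. "If the doctor has issued a UACR test for the patient, record the inspection value"; otherwise the site uses the "UACR measurement equipment provided in this study to obtain the results". Section 6.2 then puts everyone enrolled who has UACR data into one analysis set.

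**The concern.** The multiplier and the creatinine unit do not belong together. A factor of 1,000 next to 0.113 is right when creatinine is in µmol/L, but the formula says mmol/L. The output is compared directly with 30 and 300 mg/g, so a thousand-fold error changes the class of nearly everyone it touches.

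Three things depend on the result:

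- **The primary endpoint and the micro/macro split**, for every patient measured on the study device.
- **Comparability within the analysis set.** Doctor-ordered values would be on the correct scale and device values on one 1,000 times larger. Apparent albuminuria would then depend on whether a doctor had ordered the test, which would carry into the regional, disease and hospital-level comparisons and the logistic regression.
- **The physician-behaviour measures.** Sections 4.3 and 5.4 feed the calculated value back to the treating doctor and record any new order, diagnosis or prescription. A wrong value at that stage affects the recorded response itself.

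**Working it through.** **Inputs.** The formula and its units are from section 5.3. The pairs 3 mg/mmol with 30 mg/g and 30 mg/mmol with 300 mg/g are from Figure 1 in section 1.2. The cut-offs of 30 and 300 mg/g are from sections 6.3.1 and 6.4.2. The 50% prevalence, used only for illustration, is from section 6.6.

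**Step 1: what unit 0.113 has.** Figure 1 implies 3 mg/mmol ÷ 30 mg/g = 0.1 g/mmol, a rounded value. So 0.113 is the mass of creatinine in g per mmol.

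**Step 2: dimensions.** Creatinine (mmol/L) × 0.113 (g/mmol) is in g/L. Albumin (mg/L) ÷ creatinine (g/L) is in mg/g. No further factor is needed. With creatinine in µmol/L, the product with 0.113 is in mg/L, and the 1,000 is then required.

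**Step 3: can the formula reproduce Figure 1?**

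| Version | At 3 mg/mmol (Figure 1: 30 mg/g) | At 30 mg/mmol (Figure 1: 300 mg/g) |
|---|---|---|
| As written: albumin × 1000 / (mmol/L × 0.113) | 3 × 1000 / 0.113 = 26,549 | 265,487 |
| Without the 1000 | 3 / 0.113 = 26.5 | 265 |
| With the 1000, creatinine in µmol/L | 3 × 1000 / (1000 × 0.113) = 26.5 | 265 |

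Both corrected versions agree with the figure's rounded pairing. The formula as written is 26,549 / 26.5487 = 1,000 times the consistent value and 26,549 / 30 = 885 times the rounded one.

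**Step 4: where the cut-offs would act.** Dividing by 1,000, the 30 mg/g cut-off acts at a true 0.03 mg/g and the 300 mg/g cut-off at 0.3 mg/g. At an assumed creatinine of 10 mmol/L:

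- 30 mg/g is crossed at albumin 30 × 10 × 0.113 / 1000 = 0.034 mg/L, instead of 33.9 mg/L.
- 300 mg/g is crossed at 0.34 mg/L, instead of 339 mg/L.

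**Step 5: examples.** These readings are assumptions; the protocol gives none.

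| Albumin (mg/L) | Creatinine (mmol/L) | Consistent UACR (mg/g) | As written (mg/g) |
|---|---|---|---|
| 10 | 10 | 8.85 (A1) | 8,850 (A3) |
| 2 | 30 | 0.59 (A1) | 590 (A3) |
| 1 | 30 | 0.29 (A1) | 295 (A2) |

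For every combination tried with albumin 2 to 150 mg/L and creatinine 0.9 to 30 mmol/L, the formula exceeds 300 mg/g; the lowest result is 590. At albumin 1 mg/L, only creatinine 30 mmol/L fell below 300, and it still exceeded 30.

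**Step 6: share misclassified.** Assume a lognormal UACR with 50% of patients truly at or above 30 mg/g (median 30) and a log-scale SD of 1.0 to 2.0. The formula would then class more than 99.9% at or above 30 mg/g. It would class from 98.9% (SD 2.0) to more than 99.9% (SD 1.0) at or above 300 mg/g.

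**Step 7: effect on the overall prevalence.** Let d be the share of patients tested on the device, which the protocol does not give. If true prevalence is 50% in both groups and all device-tested patients are classed as cases, reported prevalence is d × 100% + (1 − d) × 50% = 50% + d × 50%. That runs from 50% at d = 0 to 100% at d = 1. The interval planned in section 6.6 is 48.2% to 51.8%, a half-width of 1.8 points. A device-tested share of 1.8 / 50 = 3.6% would already shift the estimate by that much.

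**The case against.** The best counter-argument is that this is a mislabelled unit and not a wrong calculation. The pair 1,000 and 0.113 is correct for µmol/L, so one character would explain the discrepancy. The formula was read from a PDF by a program, and other symbols in the text look damaged, so the printed page should be checked. The protocol does not say which unit the device exports or what the case report form or database computes, so it is not known that any value was or will be inflated. Section 6.1 also promises an outlier check, and values in the thousands for most device-tested patients would be conspicuous.

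Part of this stands. The harm is conditional on mmol/L readings being put through the formula as printed. It is limited to device-tested patients, and a strip albumin of exactly zero stays zero. The misclassification shares rest on assumed readings and an assumed distribution.

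The rest does not remove the point. The text gives mmol/L, and nothing else in the protocol corrects it. The general remark in section 6.1 that data will be converted where needed names neither this unit nor this multiplier. An outlier check at analysis comes after results have gone back to the doctors. Nor is this a detail left to a statistical analysis plan: it is a stated rule, used at the sites, that returns a wrong number. If the intended unit was µmol/L, the protocol still has to say so.

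**Conclusion.** The concern holds, and the formula must be corrected. As written it returns values exactly 1,000 times too high and contradicts the unit pairing in the protocol's own Figure 1. That factor follows from the units alone and needs no assumption about the data. Applied literally, it would leave the 30 and 300 mg/g cut-offs with almost no ability to separate device-tested patients: prevalence in that group would approach 100%, with nearly all cases in the macroalbuminuria class. This consequence held across every range and distribution tried. The effect on the overall prevalence depends on the share tested on the device, which the protocol does not state. Whether any real values were calculated this way cannot be told from the document.

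**What to change.** In section 5.3, make one of two changes:

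- UACR (mg/g) = urine albumin (mg/L) / [urine creatinine (mmol/L) × 0.113]; or
- keep the 1,000 and change the creatinine unit to µmol/L.

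State which unit the supplied device exports, and choose the version that matches it. Check the same calculation in the case report form and the database, and add a worked example (albumin 10 mg/L, creatinine 10 mmol/L, result 8.85 mg/g) so that sites can verify it. Recompute any UACR already calculated from the stored raw albumin and creatinine.

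Before data collection this is a one-line correction to the protocol, form and program, with no cost to patients or sites. If inflated results have already been fed back, recomputation restores the UACR values but not the doctors' recorded responses. Those records should be identified and handled separately in the analysis of physician behaviour.
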